welcomed to ask any questions. Afterwards, the experimental procedure will be explained in more detail and exemplary stimuli will be played to give the mothers-to-be an idea of what their babies will hear during the experiments. Each participant will be explicitly asked if she has any questions or concerns, and each will be reminded that the procedure can be stopped in case she feels uncomfortable or wants to withdraw. Neither of them must be justified. Afterwards, the mother-to-be will be asked if she agrees to proceed with the procedure. If she does, she will be reminded to remain silent during the experiments and to lie as still as possible to ensure a high quality of the collected data throughout the experimental parts. Next, the research team will identify foetal position as well as foetal behavioural state (after Nijhuis et al., 1982) using 2D-ultrasound. For studies 1a and 1b, the cardiotocograph (Huntleigh Sonicaid Team3) and the loudspeaker (Marshall Acton III Bluetooth Speaker) will be set-up afterwards and the participant and her whānau or friends will be given headphones before the experiments will start. To access fronto-temporal brain activity in studies 2a and 2b a particular position of the foetus will be required. As previously described, the near-infrared light of fNIRS penetrates up to 5 cm into the maternal abdomen (Araki & Nashimoto, 1992) and if the foetal head is not within this range, the participant will be asked to be taken for a short walk or to drink a glass of water to stimulate foetal repositioning. Otherwise, the experimental procedure cannot be continued, and the women will be asked to return a few days later if she is still interested in participating. If the foetus is in an appropriate position, the fNIRS probe and the loudspeaker will be put into place, headphones will be given to the mother-to-be and her company and the experiments will start.

Each session will include one timbre (studies 1a & 2a) and one chord experiment (studies 1b & 2b) which are separated by a short break in between. The specific structure of each experiment is outlined further below (paragraphs 6 & 7).

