After the completion of both experiments, the mothers-to-be will be asked if they have heard any of the stimuli and if they felt any foetal movement during the session. Everyone will be thanked for participating, debriefed, and given the opportunity to ask further questions or to comment about the studies. Every participant will be given \$ 30 vouchers in recognition of travel costs and to show appreciation of taking part in the studies. In total, each session will take about 45-60 minutes.

After participation. Following delivery, health notes of the mothers and their babies will be accessed. These include the delivery method, complications during pregnancy or birth, gestational age of the baby at birth, sex, birth weight, as well as the results of the first prenatal hearing test. The collection of these information and the reasons why they are accessed are clearly outlined in the informed consent sheet and will be brought to every participant's

attention as part of giving written informed consent. The mothers will not be contacted about this again.

The informed consent sheet further gives every participant the opportunity to sign up for getting a brief overview of the main results of all studies. These will be summed up after the data has been analysed and will be sent to all women who had requested a copy during participation.

6. Experiments 1a and 1b – HR

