Furthermore, sex, foetal HR variability (HRV) at baseline, and foetal state will be analysed exploratory in a multiple linear regression analysis to test for moderating effects. These variables were chosen based on the previous literature which has found moderating effects of foetal HRV at baseline (Lecanuet et al., 1986; 1992; Smith et al., 2007) and foetal behavioural state on foetal responses to external auditory stimuli (Devoe et al., 1990; Schmidt et al., 1985). To date, only a few studies have analysed a possible influence of sex on foetal responses. These studies have found non-significant effects (e. g. Groome et al., 1996; López-Teijón et al., 2015), but there is also evidence of sex-specific responses. Female fetuses showed a more mature response compared to male fetuses (Buss et al., 2009) as well as general foetal HR dynamics depend on foetal sex (Bernardes et al., 2007). Foetal sex will thus also be analysed exploratory as a moderating variable which is especially valuable considering the previous neglect of many studies in not analysing if female and male fetuses responded differently to the presented stimuli.

7. Experiments 2a and 2b – brain activity

Background. As summarised above, previous research on foetal auditory development and the results of foetal studies investigating cardiac responses to musical stimuli suggest that fetuses at 35-36 weeks GA have discriminatory abilities for musical stimuli. The perception and discrimination of musical stimuli can also be measured with neuroimaging techniques, such as fMRI and foetal magnetoencephalography (for review, see Dunn et al., 2015). These methods have shown mainly frontal and temporal activity after musical stimulation of the foetus (for review, see Chorna et al., 2019). For example, at 33 weeks GA, the presentation of pure

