Aims. Studies 2a and 2b use fNIRS to investigate foetal brain responses in fronto-temporal areas following the presentation of different musical timbres and chords. One aim is to find out if it is possible to measure foetal brain activity with fNIRS in general. The second aim is to see if fetuses at 35-36 weeks GA can differentiate musical timbres (study 2a) and major from minor chords (study 2b) on a cortical level.

Hypotheses.

1. It is possible to measure foetal brain activity with fNIRS.
2. Differentiating brain responses will be expected if fetuses can discriminate a clarinet, a trumpet, and a violin timbre.

Auditory Perception of the Foetus – Study Protocol

3. If foetuses can discriminate major from minor chords, this will be reflected in differentiating brain activity patterns after the presentation of major and minor chords.
4. Foetal brain activity responses within the chord categories might differ (C- vs. G- vs. D-major; a- vs. e- vs. d-minor), but this difference would be smaller than the one between the two categories (major vs. minor).

Independent variables. Study 2a: Timbre – clarinet vs. trumpet vs. violin.

Study 2b: Chord – major vs. minor.

Dependent variables. Foetal brain activity, e. g. HbO₂ and HbR.

Materials and methods - stimuli. Same as for studies 1a and 1b (see above).

Materials and methods - image acquisition. A qualified and experienced sonographer will use a Philips Epiq7 Elite Ultrasound System with either a 5C1 or 9C2 transducer (thermal index for bones < 0.3) to perform foetal check-ups, determine foetal position, foetal behavioural state, and to estimate the correct placement of the fNIRS probe. The later one will be a custom-made device consisting of one light emitter and one light detector which will be placed directly on the maternal skin. The fNIRS probe will be using two wavelengths, namely 690 nm and 830 nm, which are known to be optimal for measuring deoxy- and oxygenated blood in early developmental populations (for reviews, see Lloyd-Fox et al., 2010; Wilcox & Biondi, 2015). These wavelengths also possess the physical characteristics to enable penetration of human tissue (León-Carrión & León-Domínguez, 2012; Strangman et al., 2002). The strength of the near-infrared light will be adjusted based on the individual thickness of the maternal tissue. This will enable a consistent sensitivity to measure foetal brain activity across participants and ensure that light levels are well within boundaries for safe use.

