- age-appropriate foetal development: abdominal circumference > 5th percentile, estimated foetal weight \geq 10th percentile, and single deepest pocket \geq 2 cm (Ministry of Health, 2019)
- foetal HR is within the normal range: 120-160 bpm (Von Steinburg et al., 2013)

Exclusion criteria. Consequently, women will be excluded if they meet one or more of the following exclusion criteria:

- multifetal pregnancy
- gestational age is < 35 weeks or >37 weeks
- pregnancy complications which affect foetal HR, auditory, neuronal, or general foetal development
- maternal health issues which put either the mother-to-be or the foetus at risk or which affect foetal cardiac, auditory, neuronal, or its general development
- foetal abnormalities or health issues which affect foetal HR, auditory, neuronal, or its general development (e. g. Down syndrome)
- the foetus is small for gestational age: abdominal circumference < 5th percentile, estimated foetal weight < 10th percentile, and single deepest pocket < 2 cm (Ministry of Health, 2019)
- the foetal HR is not within the normal range: <120/ >160 bpm (Von Steinburg et al., 2013)

Because the near-infrared light only penetrates up to 5 cm into the maternal abdomen (Araki & Nashimoto, 1992), one further exclusion criteria will be applied for the fNIRS studies:

- Women will be excluded if maternal tissue thickness is > 5 cm.

Women of all ethnicities are welcome to take part in the study, ethnicity is not a criterion for participant selection.

10. Participant recruiting

We will actively cooperate with maternal health care providers and maternal health researchers to promote the present research project and to encourage pregnant women to participate in our studies. This includes, but not limits to, Hāpu Wānanga and Te Aukume a Hineteiwaiwa. Furthermore, already established contacts with midwives and birth centres will be used for participant recruitment as well as there will be a media campaign on social media

which was very successful in a previous study (Leov et al., 2023). Finally, all participants will be asked to promote the project in their whānau and to pregnant friends.

11. Remuneration/ koha

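### A single fNIRS channel on maternal skin, with no off-head reference, cannot show that a sound-locked signal is foetal, and the mother's report of hearing the sounds enters no stated analysis

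*Protocol*

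**What the plan says.** **Probe.** Protocol section 7 (image acquisition) describes a "custom-made device consisting of one light emitter and one light detector which will be placed directly on the maternal skin". It uses two wavelengths, and light strength is adapted to the thickness of the maternal tissue. No second channel, reference site or maternal recording is described.

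**Depth.** Section 5 says that the "near-infrared light of fNIRS penetrates up to 5 cm into the maternal abdomen". Section 9 sets the matching limit: "Women will be excluded if maternal tissue thickness is > 5 cm".

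**Control of maternal hearing.** Section 5 provides headphones in both sets of studies. For 1a and 1b, "the participant and her whānau or friends will be given headphones before the experiments will start"; for 2a and 2b, "headphones will be given to the mother-to-be and her company and the experiments will start". The mother is also told to stay silent and lie still. Whether the headphones play a masking sound, and how much they attenuate, is not stated. Section 8 places the loudspeaker above the abdomen.

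**Hearing report.** After both experiments, "the mothers-to-be will be asked if they have heard any of the stimuli and if they felt any foetal movement during the session".

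**Analyses.** Sections 6 and 7 specify repeated-measures ANOVAs on the stimuli. The exploratory variables for heart rate are stated as "sex, foetal HR variability (HRV) at baseline, and foetal state will be analysed exploratory in a multiple linear regression analysis"; for fNIRS they are sex and foetal state. The hearing report is in neither list.

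**Head out of range.** If a walk or a glass of water does not bring the head within reach in 2a and 2b: "Otherwise, the experimental procedure cannot be continued, and the women will be asked to return a few days later".

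**The concern.** Research question 4 and fNIRS hypothesis 1 ask whether foetal brain activity can be measured with fNIRS at all, and section 2 presents this as a proof of concept. To answer yes, the study must show that a change following the sounds comes from the foetal head and not from the maternal tissue in front of it. The planned recording holds nothing that could show this.

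A maternal response to the sounds is possible only if the mother perceives them. She has just been played similar examples, and headphones are the only barrier described. The one check on that barrier, her own report, is collected but feeds no stated analysis. A sound-locked change could therefore be announced as the first foetal fNIRS signal when it is maternal.

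**Working it through.** The plan gives no figure on this point, so the first two steps are reasoning from its text and the third is an illustration.

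**1. Can the probe tell the two sources apart?**
- One emitter-detector pair at two wavelengths gives two measurements at each moment. They are used to estimate two quantities, HbO₂ and HbR, over the whole light path. No measurement is left to apportion the change by depth.
- Stated reach of the light: 5 cm. Maternal tissue allowed: up to 5 cm. At the limit, 5 − 5 = 0 cm of reach remains for the foetal head. With thinner tissue part of the path is foetal, but the documents do not give the typical split.
- Adapting the light strength changes sensitivity, not the source of the signal.
- Averaging over the 24 presentations per timbre or chord category, and semi-random order, suppress what is not locked to the sounds. They keep a maternal response that is.

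**2. Which hypotheses are exposed?** Let F_s be the foetal and M_s the maternal response to stimulus s, and p the share of mothers who react. The expected mean signal is F_s + p × M_s.
- fNIRS hypothesis 1 (any response): if every F_s = 0, the mean response is p × M_s, which is not zero when p and M_s are not zero. A general maternal reaction is enough.
- Discrimination in 2a and 2b: the contrast is (F_1 − F_2) + p × (M_1 − M_2). A reaction common to all stimuli cancels. Bias needs M_1 ≠ M_2.
- Studies 1a and 1b: the CTG measures foetal heart rate, so a maternal reaction would first have to alter the foetal heart rate. The light-path argument does not apply.

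**3. How large could the effect on a discrimination test be?** Assumptions: no foetal discrimination; a share p of mothers shows a differential response m, in SDs of the paired difference; N = 70 (section 14, study 2b); two-sided paired t-test at 5 %, which for two chord categories equals the one-way repeated ANOVA. The documents give neither p nor m. Simulated rejection rates (20,000 runs):

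| p | m = 0.5 SD | m = 1 SD |
|---|---|---|
| 0 % | 5 % | 5 % |
| 10 % | 7 % | 13 % |
| 20 % | 12 % | 34 % |
| 30 % | 23 % | 61 % |
| 50 % | 52 % | 96 % |

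Cross-check by normal approximation: z = p × m × √N / √(1 + m² × p × (1 − p)).
- p = 0.2, m = 1: 0.2 × 8.367 / √1.16 = 1.673 / 1.077 = 1.55, a rejection probability of about 0.34.
- p = 0.2, m = 0.5: 0.1 × 8.367 / √1.04 = 0.837 / 1.020 = 0.82, about 0.13 (simulation with the t critical value: 12 %).

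**4. Length of a reference recording.** The chord sequence has 2 × 24 = 48 trials of 4.180 s: 48 × 4.180 = 200.64 s, or 3 min 20.64 s, as section 7 states.

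**The case against.** A reader might infer that a maternal reaction will be credited to the foetus and that a positive result in any of the four studies could be maternal. The documents do not support that.

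- Headphones are worn and the mother is asked to be silent and still. Nothing shows that they fail, so the risk is conditional. Nor does the post-session question prove that the sponsor doubts them; the protocol gives no reason for asking.
- In 1a and 1b the CTG reads the foetal heart, and the protocol describes no route from mother to foetus. A mother who notices a change of timbre or chord category could in principle react at that moment, but any effect would be indirect.
- In 2a and 2b the comparisons are within subject, so a general maternal reaction cancels.
- The documents do not show that abdominal tissue gives a sound-locked HbO₂ response, nor that most of the light path is maternal. A full-SD differential reaction is a severe assumption.
- An analysis using the hearing report may stand in a statistical analysis plan that is not shown.

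All of this stands and narrows the point. What it does not answer is the attribution problem in 2a and 2b. Probe geometry, the single hearing question for both experiments, and ending out-of-range sessions without a recording are fixed in the protocol. No later analysis can recover a reference that was never recorded.

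**Conclusion.** The point holds for fNIRS hypothesis 1. As designed, a sound-locked HbO₂ change in 2a or 2b would not by itself show foetal brain activity, because the single channel cannot separate foetal from maternal haemodynamics and there is no reference. Whether this leads to a false claim depends on the headphones letting sound through and on maternal tissue responding; the documents settle neither.

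For the discrimination tests in 2a and 2b the risk is smaller and needs a maternal reaction that differs by stimulus. With 20 % of mothers reacting in this way at N = 70, the illustrative false-positive rate is about 12 % to 34 % for 0.5 to 1 SD, and it stays at 5 % if none reacts. These rates rest wholly on assumed inputs and were not derived for the three-timbre test in 2a. For 1a and 1b no direct bias is shown.

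**What to change.** 1. **Use the hearing report.** Keep the question at the end of the session, so that it does not draw the mother's attention to the sounds beforehand, but ask it separately for the timbre and the chord part. Pre-specify for each study a sensitivity analysis restricted to mothers who reported hearing nothing in that part, shown beside the main result. It need not be a condition for every claim.
2. **Record an off-head reference.** When the foetal head stays out of range in 2a and 2b, run the 3 min 20 s chord sequence with the probe in place before the session ends. Claim hypothesis 1 only if the on-head response to the chords exceeds the off-head one. If too few such recordings exist, limit the conclusion to a stimulus-locked abdominal signal whose foetal origin is not shown.

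**Cost.** One question asked in two parts, one extra analysis per study, and a few minutes in sessions that would otherwise yield no data. No extra recruits are needed.

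**Downsides.** The restricted analysis is less precise, by an amount that depends on how many mothers hear the sounds. The reference group is not random, its size cannot be planned, and it covers chords only, so it is no control for 2a. Foetuses who return later will already have heard the chords, and this should be flagged in the analysis.

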Pitch perception is the first musical ability to develop which has been studied using mainly habituation and dishabituation paradigms (e. g. Hepper & Shahidullah, 1994), oddball paradigms (e. g. Holst et al., 2005), but also neuroimaging methods like functional magnetic resonance imaging (fMRI; Jardri et al., 2008). At 19-27 WG, fetuses only respond to low-frequency stimuli of 100 Hz, 250 Hz and 500 Hz. At 29-33 WG, fetuses can detect higher frequencies (around 1000 Hz) and by 31-35 WG, they respond to tones as high as 3000 Hz (Hepper & Shahidullah, 1994). As the auditory system matures, fetuses also start to respond to lower intensity levels. At 35-36 WG, first discriminatory abilities are shown between two low-frequency tones (Hepper & Shahidullah, 1994; Lecanuet et al., 2000).

Separate to pitch, rhythm perception has also been studied using habituation and dishabituation paradigms which show improved rhythm perception as development progresses. During gestation, fetuses are stimulated by and can respond to rhythms of the maternal body (e. g. heartbeat, breathing, movements), and those from the external environment, including the human voice, speech, and music (Lecanuet & Schaal, 1996; Porcaro et al., 2006; Provasi et al., 2014).

The perception and discrimination of human voices as vocal instruments have been the main subject of previous intrauterine music perception studies. These studies have reported first foetal responses to the mother's voice around the 32nd-34th WG. The recognition of the maternal voice as well as the discrimination of human voices in general improves as gestation advances (for review, see Carvalho et al., 2019). This enables the unborn child to differentiate the maternal voice from other voices at approximately 36 WG (Kisilevsky et al., 2003; Kisilevsky & Hains, 2011).

In addition to pitch, rhythm, and voice perception, tempo is also an important aspect of intrauterine music perception abilities. Fetuses between the 30th-40th WG show orientation as well as habituation patterns to different tempos in both physiological and behavioural measures (Tristao et al., 2020). Heart rate (HR) usually reflects the tempo of the stimulus with

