Aim. The aim for studies 1a and 1b is to measure foetal HR to see if foetuses at 35-36 weeks GA can differentiate musical timbres (study 1a) and major from minor chords (study 1b).

Hypotheses.

1. Foetuses will show an initial HR deceleration as part of an orienting response after stimulus onset in the first block of experiment 1a and 1b.
2. The amplitude of the initial HR deceleration will decrease over the blocks of both experiments which will reflect habituation to the presented stimuli.
3. The initial HR decrease after stimulus onset will be followed by a slower HR acceleration.
4. The HR acceleration will decrease over the course of each stimulus.
5. If foetuses can discriminate a clarinet, a trumpet, and a violin timbre, a new HR decelerative response will be expected after the first presentation of the second and third timbre in experiment 1a. This response is expected to have an increased amplitude compared to the last block of the previous timbre.
6. If foetuses can discriminate major from minor chords, a new HR decelerative response will be expected after the change to the second chord category in experiment 1b. This response is expected to have an increased amplitude compared to the last block of the previous chord category.
7. Foetal HR responses within the chord categories might differ (C- vs. G- vs. D-major; a- vs. e- vs. d-minor), but this difference would be smaller than the one between the two categories (major vs. minor).

Independent variables. Study 1a: Timbre – clarinet vs. trumpet vs. violin.

Study 1b: Chord – major vs. minor.

Dependent variables. Foetal HR variables, e. g. amplitude, absolute value.

Materials and methods - stimuli. Study 1a will investigate foetal perception and differentiation of a clarinet, a trumpet, and a violin timbre. These timbres were selected not only because they have been used in previous studies (e. g. O'Connell, 2003), but also because they represent three of the primary instrument categories, namely woodwind, brass, and (bowed) string instruments which have distinctive, category-specific temporal and spectral characteristics (e. g. Donnelly & Sheppard, 2014). All audio files have the same note (C4; pitch = 261.63 Hz), a total length of 3.492 seconds and are played at the same volume. The SPL is within the range of the ones used in previous studies and is safe for the foetal auditory system (e. g. Kisilevsky et al., 2004; Lecanuet et al., 2000; Shahidullah & Hepper, 1994). Additionally,

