a fourth file with a piano timbre was generated to match the other files in pitch, amplitude, and length which will be played to the mothers-to-be as an example for the stimuli in study 1a.

In study 1b, C-, G-, and D-major as well as a-, e-, and d-minor chords played by a piano will be used to investigate foetal perception and discrimination of major and minor chords. The chords were selected based on the results of Burgoyne et al. (2011) who reported them to be the most common chords in western popular music. Each audio file is 1.327 seconds long and the stimuli are matched for the amplitude of the sound.

The clarinet sample was provided by the University of New South Wales (Australia), the other three timbre files were given by the International Audio Laboratories Erlangen (Germany), and the chord stimuli were downloaded from auralwiz.com. All audio files were used and altered with permission of the copyright holders.

Materials and methods - image acquisition. A qualified and experienced sonographer will use a Philips Epiq7 Elite Ultrasound System with either a 5C1 or 9C2 transducer (thermal index for bones < 0.3) to perform foetal check-ups, determine foetal position, foetal behavioural state, and to ensure the correct placement of the CTG. A Huntleigh Sonicaid Team3 CTG will be used to measure foetal HR four times per second using a directional pulsed Doppler Ultrasound transducer.

Each session will be recorded and saved on two external hard drives as well as stored in a secure folder on the university server for later analyses.

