
Each session will be recorded and saved on two external hard drives as well as stored in a secure folder on the university server for later analyses.

Procedure. The experimental procedure of the two studies will be explained to the participant after giving written informed consent and after foetal check-ups have been performed. Two exemplary trials of each of the two experiments will then be presented. These are a C4 played by a piano for study 2a and one trial each with a F-major and a f-minor chord for study 2b. Both are also played by a piano. After the participant confirms that she has no further questions and agrees to move on to the actual experiments foetal position and behavioural state will be identified. Then, baseline 1 will follow and experiment 2a will start thereafter. The three different timbres will be presented 24 times each in a semi-randomised order. Thus, unlike to

experiment 1a no block-design will be used which is also true for experiment 2b. A semi-randomised presentation of the stimuli was chosen because fNIRS is an event related measure of brain activity. This means that brain activity can be measured every time a change in the environment takes place. Every trial of study 2a includes 3.492 seconds of sound and is 11 seconds long (ratio 1:2.15). The whole experiment will take 13 minutes and 12 seconds. Afterwards, a brief break will follow. Then, baseline 2 will start and the chord stimuli will be presented thereafter. Both major and minor chords will be presented 24 times which means that each individual chord will be played eight times, also in a semi-randomised order. All trials are 4.180 seconds long and include 1.327 seconds of sound plus 2.853 seconds ISI (ratio 1:2.15). Experiment 2b is 3 minutes and 20.640 seconds long.

The order of the stimuli will be counterbalanced across participants in both experiments.

Data analyses. Foetal brain activity will be analysed in two separate one-way repeated ANOVA to compare foetal responses to the three different timbres (study 2a) as well as between major and minor chords (study 2b).

Degrees of freedom will be adjusted if the assumption of sphericity is violated in either of the analyses. Post hoc comparisons will be done with Tukey tests ($p < .05$) and Bonferroni-correction will be used for α -adjustment to take multiple comparisons into account.

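### The major and minor chord sets share only one root, so the planned major-versus-minor contrast in studies 1b and 2b mixes mode with root pitch

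*Protocol*

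**What the plan says.** Protocol section 6 (stimuli) fixes the chords as "C-, G-, and D-major as well as a-, e-, and d-minor chords played by a piano". They were picked because a cited study "reported them to be the most common chords in western popular music". On acoustic matching it says: "Each audio file is 1.327 seconds long and the stimuli are matched for the amplitude of the sound". No matching of root, octave or voicing is stated. The timbre stimuli are held at one pitch: "All audio files have the same note (C4; pitch = 261.63 Hz". The example chords played to the mothers, F-major and f-minor, do share a root. Section 7 uses the same stimuli.

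Sections 6 and 7 name major against minor as the only independent variable for chords. HR hypothesis 6 says that, if foetuses can tell major from minor, "a new HR decelerative response will be expected after the change to the second chord category in experiment 1b"; fNIRS hypothesis 3 makes the parallel statement for brain activity. HR hypothesis 7 and fNIRS hypothesis 4 allow for differences among chords of one category, "but this difference would be smaller than the one between the two categories (major vs. minor").

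The analyses are a two-way repeated ANOVA in 1b, with the second factor not named, and a one-way repeated ANOVA of major against minor in 2b. In 2b, "each individual chord will be played eight times, also in a semi-randomised order".

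On pitch, section 1 says that at 35-36 weeks "first discriminatory abilities are shown between two low-frequency tones". The section 6 background adds that 90 % of the foetuses (36-39 weeks) that decelerated to one note decelerated again to a second.

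**The concern.** Research question 3 and the chord part of question 5 ask about major against minor. A difference between the category means, or a renewed deceleration at the category change, would be read as an answer. Two of the three roots change with the category, however, and the protocol's own background shows that a change of note can by itself produce a response near this age. A positive chord result could then reflect root pitch, wholly or in part. Counterbalancing does not help: it varies the order, but the same roots stay in the same category in every order. Hypotheses 7 (HR) and 4 (fNIRS) point at the right check, but no named factor or test carries them.

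**Working it through.** **1. The protocol's own figures.** Section 14 gives f = 0.1, power 0.95, α = 0.05, ρ = 0.50. The repeated-measures formula is λ = f²·N·m/(1 − ρ), df1 = m − 1, df2 = (N − g)(m − 1).
- HR chord experiment (1b, although section 14 labels it 2b), m = 30: λ = 0.01 × 60 × 30/0.5 = 36, power 0.953. N = 60 is reproduced.
- fNIRS chord experiment, m = 24, g = 2: N = 70 is reproduced, power 0.957.

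No stated figure is in dispute here.

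**2. What the category contrast estimates.** Write each chord mean as mode effect + root effect.
- Major mean = major + (C + G + D)/3
- Minor mean = minor + (A + E + D)/3
- Difference = (major − minor) + (C + G − A − E)/3

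D cancels; the other four roots do not. If root is added to the model, six chord means support six parameters, and the mode effect is estimated only by D-major minus d-minor.

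**3. Size of the pitch difference.** In semitones above C, within one octave, the roots are 0, 7, 2 (mean 3) for major and 9, 4, 2 (mean 5) for minor, a difference of −2. Moving a chord by an octave shifts this by 12/3 = 4, so the possible values are ±2, ±6 and so on, never 0. Averaged over all nine notes per set, the difference can be as small as (48 − 51)/9 = −1/3 semitone.

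**4. Shared notes (of three).**
- Between categories: C-a 2, C-e 2, C-d 0, G-a 0, G-e 2, G-d 1, D-a 1, D-e 0, D-d 2. Mean 10/9 = 1.11.
- Within categories: C-G 1, C-D 0, G-D 1, a-e 1, a-d 1, e-d 0. Mean 4/6 = 0.67.
- Taken whole, each set uses seven pitch classes and six are common; only F♯ (major) and F (minor) differ.

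**5. Why a test of hypothesis 4 is informative.** Suppose responses followed root pitch alone, with the one-octave roots of step 3. The mean root distance is (9+4+2+2+3+5+7+2+0)/9 = 34/9 = 3.78 semitones between categories and (7+2+5+5+7+2)/6 = 28/6 = 4.67 within. Within-category differences would then be the larger, the reverse of hypothesis 4.

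**6. Illustration.** A simulation with no mode effect assumed N = 60, 10 presentations per chord, ρ = 0.5, one-octave voicing and a response linear in root pitch:

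| Slope (SD per semitone) | Category test rejects |
|---|---|
| 0 | 5 % |
| 0.01 | 14 % |
| 0.02 | 38 % |
| 0.03 | 73 % |
| 0.05 | 99 % |

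The D-major versus d-minor test stayed near 5 % throughout. The slopes are assumptions; nothing in the protocol says which applies.

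**7. Cost of using only the D pair.** Same formula, g = 2:
- 2b, m = 8 (stated), N = 70: λ = 0.01 × 70 × 8/0.5 = 11.2, power 0.67; 95 % power needs N = 138.
- 1b, m = 10 (assumes 30 presentations split equally over three chords), N = 60: λ = 12, power 0.65; at N = 84, 0.83; 95 % power needs N = 120.

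These figures follow the protocol's convention of entering presentations as m.

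**The case against.** The strongest reply is that the pitch rival is weaker than it looks. Chords within a category share fewer notes on average (0.67) than chords across categories (1.11), and the sets have six of seven pitch classes in common. If 1b blocks mix chords, the category change brings in only one new pitch class. The background evidence concerns single tones, and the one interval identified, D4 to C5, is wide. This stands. A reader might infer that pitch explains a positive result as well as mode does, or that such a result would be an artefact. The documents support neither, since voicing and octave are not given.

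Second, any change from major to minor alters a pitch: D-major to d-minor moves F♯ to F. That is also right. The D pair removes the root difference, not every pitch difference.

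Third, HR hypothesis 7 and fNIRS hypothesis 4 already set within-category against between-category differences, the unnamed factor in 1b might serve them, and details may lie in a SAP. In part this stands: the idea is there. But individual chord is not among the independent variables, the 2b ANOVA is stated as one-way on category, and the stimuli and hypotheses are fixed in this protocol.

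Finally, the chords have a stated rationale. It explains why they were chosen but does not separate mode from root.

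**Conclusion.** The point holds as a limit on interpretation. That the category contrast equals mode plus (C + G − A − E)/3 of the root effects is algebra, given additive effects, and applies to both 1b and 2b. Root pitch is a credible alternative on the protocol's own background, and the category ANOVA cannot exclude it. The size of the bias is unknown; the simulated rejection rates rest on assumed slopes and one-octave voicing. It would also be wrong to say that the design has no way to separate the two: D-major and d-minor are root-matched, at reduced precision, and hypothesis 4 is a useful check once a test is attached. As written, a significant category effect supports discrimination of these two chord sets, not of major and minor as such.

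**What to change.** - **2b:** model individual chord within category. Attach a test to hypothesis 4, for example the mean absolute difference over the nine between-category pairs minus that over the six within-category pairs, per foetus. Every chord has eight presentations, so both sides carry similar noise. Report D-major versus d-minor with its confidence interval.
- **1b:** keep the block design and record the chord order. State whether a block holds one chord or several. Do the same analyses where the order allows. If chords are mixed within a block this may not be possible: a chord starts every 1.327 + 1.673 = 3 seconds, while section 6 cites HR changes peaking about 5 or 10-20 seconds after onset.
- **Both:** state octave and voicing. Claim major/minor discrimination only if these results support it; otherwise word the conclusion as discrimination of the two chord sets.

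Two tempting alternatives are not advised. Requiring only that the D/d contrast has the same sign as the category effect would let through about half of spurious effects. One chord per block in 1b would disturb the habituation and last-block comparisons.

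The cost is wording and added model terms; no new stimuli or participants are needed. The D/d contrast uses one third of the chord trials, so it is supportive, not confirmatory.
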